The CaP TB project is a 4-year (October 1, 2017-September 30, 2021) Unitaid-funded project implemented by EGPAF (in sub-Saharan Africa) and SAATHII (in India) to improve pediatric TB outcomes by introducing models of care and strengthening access to WHO-recommended drugs and diagnostics. EGPAF and SAATHII, through the CaP TB project will develop, implement, and document innovative models of pediatric TB care focusing on integration, decentralization, and community-based care. Integration refers to supporting TB activities, such as screening and TB sample collection for children, into non-TB health care services, such as general pediatric outpatient clinics. Decentralization refers to moving pediatric TB services from higher levels of health clinics to lower levels. Community-based care refers to care that is delivered outside the facility, often, but not exclusively, at household level. We hypothesize that such models of care will increase case detection and care delivery, thus improving key pediatric TB outcomes. CaP TB focuses on the regions with the largest contributions to pediatric TB: AFRO and SEARO. The CaP TB countries where the project and project evaluation will be carried out are: Cameroon, Cote

d'Ivoire, DRC, Kenya, Lesotho, India, Malawi, Tanzania, Uganda and Zimbabwe.

Innovative models of care will include integration of TB services into MNCH, HIV, nutrition, and other key pediatric health care entry points. CaP TB will also support improved intensified community case finding including through contact tracing of adult and pediatric index TB patients, optimized clinical-radiological diagnosis, increased uptake of molecular diagnostics, and where feasible, decentralized or community-based initiation of TB preventive therapy. CaP TB will not be altering treatment algorithms for TB preventive therapy or for those with active infection, but will be following national guidelines or MOH guidance to the project as to the type and duration of treatment provided.

a) *Figure 1: Intensified Case Finding & Integration of Services*

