In each site, trained data collectors will retrospectively extract data from appropriate registers, logs, and in some cases patient files, for a period of 12 months starting 6 or more months before the start date of data extraction. This time frame has been selected in order to allow to accurately measure indicators on treatment completion for both drug-sensitive TB treatment and preventive therapy (treatment lasts 6 months in both cases). In certain cases, the data sampling frame will start more than 6 months before the data extraction if CaP TB interventions had started during the sampling frame. Thus the sampling frame was chosen so that the end date of retrospective pre-intervention data abstraction would be before the start of any intervention to ensure that the baseline data was not affected by the early activities. For some indicators, baseline data will not be available in existing registers or logbooks. Data collectors will extract data from all pediatric entry points within the facility, including MNCH, HIV, nutrition and other relevant pediatric health care entry points. Only required variables will be abstracted and entered into the password-protected computers. Data with the patient date of birth (DOB), patient ID (if any), TB treatment ID and preventive treatment ID will be collected. The patient ID (if any), TB treatment ID and preventive treatment ID will all be encrypted before being uploaded into the CaP TB Database Entry Tool. DOB will be abstracted in order to facilitate tracking across registers if needed, as well as for data quality assurance purposes. This information will only be used to link registers. Only de-identified patient data will be abstracted into our global project

database. No other unique identifiers such as contact details of the children or their caregiver will be abstracted from the registers. Data from included pediatric patients will be extracted from the registers and recorded in the CapTB Baseline Data Abstraction form from where the data will be entered into a CaP TB Database Entry Tool (Excel-based and/or Web/mobile App-based) developed for pre-and post-intervention data , in a password protected computer and/or Android device (See Annex A: CapTB Information System).

The target population for the pre-intervention assessment is the records of any pediatric patient (0-14 years of age) who attend one of the sub-set of pilot sites in any of the 10 CaP TB countries who receive TB services. TB services include:

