- Screening for TB (clinical symptoms or signs)
- Receiving services (such as contact tracing) as a result of being a contact of a TB index case
- Clinical diagnostic assessment for TB
- Microbiologic diagnostic assessment for TB
- Treatment for active TB
- TB preventive therapy

Data collection of pre-intervention baseline data will take place prior to the start of CapTB interventions or immediately after, ensuring that the calculated data abstraction period does not overlap with any of the early project interventions. Data collection in each site may last up to 4 days and in some cases data collection may last several days longer.

VI. Evaluation Design and Methods

CaP TB implementation data will be collected by project-specific data collection tools and/or from existing registers. Whenever possible, the CaP TB data collection will use existing site level data collection tools to gather the data for the project. However, where such tools do not exist or the tools have gaps to capture all the necessary indicators, we will introduce project-specific data collection tools, the Pediatric TB Intensified Case Finding Screening Tool (ICF tool), the CaP TB Pediatric TB Form and any other form that may evolve as we learn lessons from project implementation.

Use of project-specific data collection tools

As part of the CaP TB intervention, healthcare workers will fill out a Pediatric TB Intensified Case Finding Screening Tool (ICF tool). This tool has no identifying information and will provide information on 1) number of children screened for TB in each healthcare entry point (e.g. pediatric ward, outpatient department, MNCH clinic, and nutrition clinic); 2) sex of the child; 3) age of the child; 4) if the child has any signs of symptoms concerning for TB (according to WHO guidance); 5) if the child is a contact of a TB case; and 6) the date of screening. The forms are also color coded according to the healthcare entry points where children are seen (White= MCH/PMTCT; Blue= outpatient department; Pink= Nutrition; Yellow= Pediatric Ward, Other=to be decided). See Attachment: Pediatric TB Intensified Case Finding Screening Tool.

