For children with presumptive TB: For all patients with a positive TB screen (children who have signs and symptoms concerning for TB according to the left side of the ICF tool), or for children who are a household contact of a TB case, the CaP TB Pediatric TB Form will be used to collect data on TB clinical and bacteriological investigations, as well as treatment initiation information at patient level. In addition, this form will be used directly to screen for TB symptoms in HIV clinics and during screening of contacts of TB index cases in the community, instead of the ICF tool for those 2 entry points, in effort to minimize unnecessary duplication of data entry. This CaP TB Pediatric TB Form will be adapted to country-specific requirements in collaboration with the MOH. This form will be printed on quadruplicate carbonated multi-colored papers (See Attachment C: CapTB Pediatric Form).

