Project data sample size: As this is a project evaluation, no specific sample size has been calculated. However, we estimate that the project will increase case detection by 2-fold and result in an additional 16,471 pediatric TB cases being treated.^{xxxix} This is based on an assessment of the number of children we project to screen (both HIV positive and HIV negative) in our project sites throughout the project. From the literature, we estimate that approximate Number Needed to Screen (NNS) to identify 1 TB case is 41 children. Assume that Number Needed to Screen (NNS) to identify 1 TB case is 41 (estimated NNS when symptom based screening is the only primary screening done)^{xl, xli}. Preventive treatment coverage is estimated to increase by four-fold, with an additional 52,317 children to be initiated on preventive therapy. This is based on the estimated number of child TB contacts we will identify through contact tracing plus HIV-infected children who qualify for preventative treatment.

To compare pre- and post-intervention outcomes, we will use either the ratio of the two proportions (relative risk) or the difference between the two proportions (risk difference). We will use Z-tests to assess the statistical significance of the estimated effect of CaP TB.

For measuring turn-around-time (TAT) between when a child is identified as a presumptive TB case and when the child is diagnosed with TB and the TAT between when a child is diagnosed as a presumptive TB case and when the child initiates TB treatment, if the TATs are approximately normally distributed, we will use the paired t-test to assess for statistical significance, otherwise we will use the Wilcoxon rank sum non-parametric test.

A. Quality Assurance

All data collectors will be trained in quantitative data collection by EGPAF staff. Prior to training, all data sources, abstraction and collection tools and procedures will be reviewed and tested. The HQ EGPAF team will provide on-going support to in-country teams throughout program implementation and all data collection activities.

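### Yield proportions and turnaround times are compared before and after without regard to entry point, although the project changes the mix of entry points, so a crude fall in yield or longer turnaround need not mean worse care

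*Combined protocol and SAP*

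**What the plan says.** The intervention is partly a change in where children are screened. Section IV.A.1 states: "Innovative models of care will include integration of TB services into MNCH, HIV, nutrition, and other key pediatric health care entry points". It also adds community case finding through contact tracing. Section VI has the project form used directly in HIV clinics and "during screening of contacts of TB index cases in the community".

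The baseline (Section V.A) is retrospective: "Data collectors will extract data from all pediatric entry points within the facility". That sentence goes on to name MNCH, HIV and nutrition, and the baseline population includes children reached as contacts. Table 1 lists contact-tracing records as a baseline source where they exist.

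For the comparison of proportions, Section IX says "we will use either the ratio of the two proportions (relative risk) or the difference between the two proportions (risk difference"), tested with Z-tests. Turnaround times get a paired t-test or a Wilcoxon rank sum test. No stratification, standardisation or adjustment is named.

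Entry point is recorded after launch, at least on the screening tool: "The forms are also color coded according to the healthcare entry points where children are seen". The only planned split by entry point that I found is for preventive-therapy starts in the cost-effectiveness data (Section VII.A).

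**The concern.** Four primary-objective indicators (Section II.B) depend on who enters the denominator or when the clock starts: b (presumptive among screened), e (diagnosed among presumptive), and g and i (time from presumptive identification to diagnosis and to treatment). Secondary objective (a) compares them with baseline.

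A crude before/after contrast mixes two things: a change in the share of children coming from each entry point, and a change in what happens to a child at a given entry point. Screening more children in settings with lower TB prevalence reduces the overall yield even if no setting performs worse. Section V acknowledges secular trends and relies on long duration and large size to mitigate them. Neither helps here, because the project itself causes the shift in mix, and more data only make the resulting difference more significant.

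Turnaround has a second weakness. Table 1 takes the baseline dates from registers and the later dates from the project form and/or registers. The form is opened at the positive screen (Section VI). The documents do not say which recorded event fixes the presumptive date in each period.

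**Working it through.** **The plan's own figures.** Section IX says "As this is a project evaluation, no specific sample size has been calculated", so there is no power calculation to reproduce. It projects: "we estimate that the project will increase case detection by 2-fold" and "result in an additional 16,471 pediatric TB cases being treated", with a number needed to screen of 41. That implies 16,471 × 41 = 675,311 additional children screened. The documents give no number to be screened, so the projection can be neither confirmed nor refuted.

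**Step 1: what the 2-fold target implies for indicator e.** Let R be the ratio of presumptive children after to before. If diagnosed cases double, the relative risk (RR) for diagnosed among presumptive is 2/R:

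- R = 1.5: 1.33
- R = 2: 1.00
- R = 3: 0.67
- R = 4: 0.50

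It falls below 1 whenever presumptive children more than double.

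**Step 2: would the planned Z-test call this a fall?** Table 3 gives a floor of 5 presumptive children per clinic and 10 to 20 sites in each of ten countries: 5 × 10 × 10 = 500 to 5 × 20 × 10 = 1,000. Take n₁ = 1,000, R = 3 and an assumed baseline yield of 20%. Then p₂ = 400/3,000 = 0.133, the pooled p = 600/4,000 = 0.15, and z = (0.133 − 0.20)/√[0.15 × 0.85 × (1/1,000 + 1/3,000)] = −5.1. With assumed baseline yields of 10% and 30%, z = −3.5 and −6.6. At the floor of 500, z = −2.5, −3.6 and −4.6 for 10%, 20% and 30%. These treat children as independent.

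**Step 3: can mix alone produce this?** Assume 1,000 presumptive children at baseline, 800 from a high-yield and 200 from a low-yield group of entry points. Both groups are present in both periods and the yield within each never changes. The high-yield group stays at 800, and cases double only through more low-yield children. The yields are assumptions.

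| Yield high/low | Before | After | Crude RR | Mantel-Haenszel RR |
|---|---|---|---|---|
| 30%/5% | 250/1,000 | 500/6,000 | 0.33 | 1.00 |
| 30%/10% | 260/1,000 | 520/3,600 | 0.56 | 1.00 |
| 20%/10% | 180/1,000 | 360/2,800 | 0.71 | 1.00 |
| 20%/15% | 190/1,000 | 380/2,267 | 0.88 | 1.00 |
| 20%/20% | 200/1,000 | 400/2,000 | 1.00 | 1.00 |

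First row: before, 800 × 0.30 + 200 × 0.05 = 250. After, 240 cases from the high-yield group leave 260 to find at 5%, which needs 5,200 children. The artefact vanishes only when yields are equal.

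**Step 4: indicator b.** Assume 1,000 children screened at baseline, 20% presumptive. Afterwards the same settings screen 1,000 at 22%, and other settings add 9,000 at 5%. The crude proportion is (220 + 450)/10,000 = 6.7%, RR 0.067/0.20 = 0.34. With only 1,000 added it is (220 + 50)/2,000 = 13.5%, RR 0.68. The like-for-like RR is 0.22/0.20 = 1.10.

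**Step 5: turnaround.** A crude mean is the mix-weighted average of entry-point means, so it moves with the mix in the same way. Separately, if the recorded start moves c days earlier while the true gain is g days, the apparent change is c − g. With an assumed g = 2, c = 0 shows −2 days, c = 2 shows 0 and c = 5 shows +3.

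**The case against.** **Pooling is inferred from silence.** Section IX names effect measures and tests; it does not say that entry points will be pooled, and Section XIV assigns a statistical analysis plan still to be developed. This stands as a limit on what can be claimed, but the method as stated is crude, and the later plan is a natural place to say otherwise.

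**A reader might infer that MNCH, nutrition and contact-traced children enter only the later period.** The documents do not show this: Section V.A and Table 1 include these sources at baseline, contact tracing where records exist. What changes by design is the amount of screening in each. Step 3 needs no post-only group.

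**A reader might infer that the baseline clock starts when a sick child reaches a TB unit.** That appears nowhere. Indicators g and i are defined identically in both periods, and where project tools are not used, Section VI takes later data from registers as at baseline. A shift is possible because the source changes, but it is not established.

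**The whole-facility comparison is legitimate.** Reaching more entry points is the intervention, so the overall contrast is a total programme effect. Removing new entry points from it would discard part of what the project does. This objection succeeds against replacing the crude comparison, but not against adding one beside it.

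**Key indicators.** Those in Section V.A are the number diagnosed, treatment success, and preventive therapy started and completed. Indicators b, e, g and i are not among them. This limits the stakes.

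**Stratification is imperfect.** If screening within one entry point went from selective to universal, the same distortion persists inside that stratum. This also stands.

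**Conclusion.** The point holds in conditional form. As written, Section IX cannot separate a change in who is screened from a change in care for indicators b, e, g and i. If the 2-fold target is met in the compared sites over equal periods and presumptive children triple, the relative risk for e is 0.67, and at the plan's minimum baseline numbers the Z-test would probably declare it significant (power 67% to above 99% over assumed baseline yields of 10% to 30%, two-sided 5% level assumed). With assumed yields, a change of mix alone gives anything from 0.33 to 1.00.

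The documents do not support saying that yield will fall or turnaround will lengthen. They give no yield or time by entry point, and if presumptive children less than double while cases double, yield rises. All entry-point yields, and the days in the turnaround example, are assumptions. The count of children diagnosed is untouched. This should be corrected before analysis; it does not undermine the evaluation's main case-finding result.

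**What to change.** In Section IX, or in the analysis plan that Section XIV foresees:

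1. Keep the whole-facility comparison, labelled as the total programme effect.
2. Add a before/after comparison of b, e, g and i within entry point, at sites and entry points with data in both periods. Pool across sites, for example within country, and summarise by weighting to the baseline entry-point mix or, for the proportions, by Mantel-Haenszel.
3. Report entry points with no baseline screening as post-only results.
4. State that a fall in the crude proportion alone will not be read as worse performance.
5. Name one recorded event as the presumptive-identification date and use it in both periods.

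The cost is analysis wording, plus an entry-point code in the database if the project form does not already carry one. The real limit is data. The colour-coded screening tool has no identifiers and is collated as aggregates, while e, g and i come from the form or registers. Section V.A does not promise an entry point per child at baseline and warns that some baseline data will be unavailable. Results for e, g and i will therefore be restricted to records that carry it. Strata will be thin: with six entry points (HIV, ward, outpatient, MNCH, nutrition, contact tracing), the floor of 5 presumptive children per clinic averages 5/6 = 0.8 per entry point per site. With 10 to 20 sites per country that becomes 50/6 ≈ 8 to 100/6 ≈ 17 per entry point, which is why pooling across sites is needed.

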PMTCT	Prevention of Mother to Child Transmission
PT	Preventive therapy
PTB	Pulmonary TB
QA	Quality Assurance
RIF	Rifampicin
SAATHII	Solidarity and Action against the HIV Infection in India
SEARO	WHO Southeast Asia Regional Office
SIE	Strategic Information and Evaluation
SOP	Standard Operating Procedure
TA	Technical Advisor
TAT	Turn Around Time
TB	Tuberculosis
Xpert	GeneXpert
WHO	World Health Organization

I. Rationale & Background Information

Tuberculosis (TB) in children is often missed or overlooked due to non-specific symptoms and difficulties in diagnosis. This has made it difficult to assess the actual magnitude of the childhood TB epidemic, which may be higher than currently estimated.^I Due to this paucity of data, the extent of TB in children remains largely unknown.^{II} In 2016, the World Health Organization (WHO) estimated that over one million children (<15 years) suffer from TB worldwide. With over 201,000 child deaths globally in 2016, including 52,000 among HIV/TB co-infected children, TB is a top ten cause of death in children. HIV co-infected children and the general population of children under five years of age (irrespective of HIV infection) are also at higher risk of pediatric TB.^{III}

Significant gaps exist across the entire cascade of care for pediatric TB including prevention, screening, diagnosis and treatment for pediatric TB. Globally, only 39% of pediatric TB cases are notified to national TB programmes (NTPs), with the remaining children undiagnosed or unreported.^{IV} Those who are not diagnosed experience high case fatality rates of 50% or more.^V ^{VI} A recent analysis of the cascade of care for pediatric TB in Kenya and Uganda demonstrated that only 20% of the estimated pediatric TB cases in the cohort completed TB treatment, with the largest shortfall being in diagnosing patients.^{VII}

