The CaP TB Pediatric TB Form will also be used for referral for an initiation of TB preventive therapy, primarily during contact tracing or screening at HIV clinics. The relevant healthcare worker will fill the section "To be filled by requesting health worker" and the section "To be filled during contact tracing and in HIV clinic only." These sections contain identifying information of the pediatric patient, contact information and information on eligibility for TB preventive therapy. If the child was identified at the HIV clinic, the healthcare worker keeps the last copy (pink) and the child/caregiver will bring with him/her the three remaining copies of the carbonated form and gives them to the unit initiating PT. If the child was identified through

contact tracing in the household, the community health worker (CHW) gives the last copy (pink) to the patient or patient’s caregiver and the CHW brings the remaining 3-copy form to the TB unit. When the patient presents to the facility for TB preventive therapy initiation, the healthcare worker initiating TB preventive therapy will complete the section “To be filled by HCW providing PT.” This section contains information on TB preventive therapy initiation, date of initiation and the patient’s preventative therapy register number. In the event that the initiation date is not recorded, an EGPAF data collector will be responsible for following up with the entry point or facility providing TB preventative therapy. Upon completion of the form, one copy will remain at the facility (1st page) and the data entry copy (2nd page) will be transferred to the EGPAF office for entry into the project database.

CaP-TB data collector will ensure timely data collection and reporting from all CaP-TB sites. This copy is the project’s data collection form. The form that data collectors will be collecting has all identifying information for the patient blocked out, except the child ID (if any), the TB treatment register number (or TB preventive therapy register number), the sex, and the date of birth to protect patient confidentiality.

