To this aim, EGPAF will sub-contract University of Sheffield, key leader in childhood TB health economic modelling, to perform a cost-effectiveness analysis (CEA). The resulting effects estimates will be based on routinely collected project intervention country-level aggregates from key indicators describing the cascade of care, as well facility-level data for the comparison of the pre- and post- project intervention phase. All data to be used will have already been collected through TIPPI Pre-Intervention evaluation (described in section V, subsection A) and CaP-TB implementation evaluation (described in section V, subsection I).

Only aggregated clinical data will be shared with University of Sheffield and thus considered for the CEA analysis, as described below:

- i. Averaged monthly rates per site (including absolute numerator and denominator) of pediatric (children aged 0-14 years) TB notifications, DS-TB initiations, and PT initiations for a subset of sites for which both baseline and prospective data have already been collected (restricting to sites where data on both periods are available).
- ii. Country-aggregated project intervention numbers of: a) Children screened for TB, b) Children identified as presumptive TB, c) Children with presumptive TB tested with Xpert, d) Children diagnosed with TB, e) Children treated for DS-TB, f) All TB index cases for whom successful contact tracing has been done, g) Children started on TB Preventive Therapy (disaggregated by HIV and Contact investigation entry points), and h) Sites contributing to the country-level dataset.

All patient-level indicators mentioned in points i and ii above are included in Table 1. The cost-effectiveness analysis will use pre-intervention and project intervention data, with the potential for sub-analysis of shorter targeted period during the intervention phase.

The final cost-effectiveness analysis outcomes are expected to be reported by country, and individual countries will be identified to allow to use context-specific results to inform decision-making.

The costs will be estimated as follows:

- Core health services costs will be derived from published literature.
- CaP TB intervention costs will be estimated based on EGPAF CaP TB budgets and expenditure data from EGPAF's financial system.
- EGPAF country team staff will assist in allocating cost items to specific activities within the CaPTB cascade of service delivery.

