Aggregated data will not contain any identifiable information about clients and there is minimal potential for a breach in confidentiality. Additionally, patient level data abstracted for pre and post-intervention analysis will be aggregated for dissemination of findings to further protect confidentiality and will not contain any identifiable information about patients. The CaP TB Database Entry Tool will be located on a password-protected computer and/or Android device. The name of the patient and their caregiver, contact details and other identifiable information such as addresses, phone numbers will not be entered into the CaP TB Database Entry Tool at any time.

Only the health facility staff will have access to the identification number that links the ID to the patient's name and other identifiable patient information such as caregiver's name and address, TB Prevention therapy number, TB treatment number and patient identification numbers (if available) will be automatically encrypted before upload to the global database, so that upon review at headquarter level, an evaluation identification number is assigned to all children.

However, to protect the confidentiality of the patient, we will implement the following protective measures:

- a) At the country level, patient information, including the patient ID (if any) and treatment register numbers will be entered into the country CaP TB Database Entry Tool, and will be automatically encrypted, with the exception of DOB, before uploaded into the project database.
- b) The database with global data is housed in Microsoft cloud. The database developers, the Diagnostics Advisor and the Senior Strategic Information and Evaluation Officer and other key relevant staff such as the Senior Biostatistician responsible for data analysis, have access to all the country files, globally. These are the files that contain the patient IDs. Access to the database is password protected and access to this file can only be provided by the database developer.
- c) All calculations are done on the backend of the database system, including the count of unique number of patients; the dashboard which is the project's data visualization tool, presents aggregated data without patient IDs or treatment register numbers.
- d) The CaP TB Pediatric Form ID Number, generated by the project, will be made visible and will be used to track records with data quality errors.

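### Age is recorded in both periods, but one sentence confines baseline date of birth to register linkage and every planned comparison pools ages 0-14, so a change in age mix cannot be told apart from a change in care.

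*Combined protocol and SAP*

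**What the plan says.** **Collection.** For the baseline, Section V.A states: "Data with the patient date of birth (DOB), patient ID (if any), TB treatment ID and preventive treatment ID will be collected". After the intervention starts, Section VI keeps on the data-entry copy of the form, among a few other items, "the sex, and the date of birth to protect patient confidentiality". Section X says that patient and register numbers "will be automatically encrypted, with the exception of DOB, before uploaded into the project database". The project database therefore holds date of birth in usable form.

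**Permitted use.** Section V.A first gives two purposes: "DOB will be abstracted in order to facilitate tracking across registers if needed, as well as for data quality assurance purposes". The next sentence says "This information will only be used to link registers". The two do not agree, and the restriction appears only in the baseline section.

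**Analysis.** Section II.B defines the indicators for children 0-14. Section IX compares the periods by the ratio or difference of two proportions with Z-tests. It names no age strata and no adjustment.

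**Cost-effectiveness inputs.** Section VII.A lists per-site monthly rates of "pediatric (children aged 0-14 years) TB notifications, DS-TB initiations, and PT initiations", and country totals whose only patient-level split is preventive-therapy starts by HIV or contact-investigation entry point.

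**Age as a factor.** Section I notes that "children under five years of age (irrespective of HIV infection) are also at higher risk of pediatric TB" and mentions the difficulty of obtaining sputum from under-fives. Table 2 splits baseline household contacts by age, but only for setting targets.

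**The concern.** This is a non-randomised before-and-after comparison, and the intervention changes where children are found: "Innovative models of care will include integration of TB services into MNCH, HIV, nutrition, and other key pediatric health care entry points". If that alters the age mix of children tested, diagnosed or treated, and the outcome differs by age, a crude proportion moves even when care is unchanged within each age band. Treatment success and preventive-therapy start and completion are among the four key indicators in Section V.A, so a misreading there would bear directly on the main conclusions. Section V discusses secular trends as a threat to the comparison but not case mix. The cost-effectiveness results are to be reported by country to inform decisions, and they would start from inputs in which age cannot be seen.

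**Working it through.** **Inputs.** The documents give no age distribution, age-specific outcome, sample size or significance level, so there is no planned figure to reproduce. All values below are assumed, except the doubling of case detection (Sections III and IX).

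**Formula.** Let w0 and w1 be the under-five share before and after, and let pU and pO be the outcome proportions at 0-4 and 5-14, held equal in both periods (zero true effect).

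- Crude proportion = w × pU + (1 − w) × pO
- Spurious risk difference = (w1 − w0) × (pU − pO)

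**Success-type outcome, w0 = 40%.**

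| w1 | 75% vs 85%: before → after | Difference (ratio) | 80% vs 85%: before → after | Difference (ratio) |
|---|---|---|---|---|
| 40% | 81.0 → 81.0 | 0 (1.00) | 83.0 → 83.0 | 0 (1.00) |
| 50% | 81.0 → 80.0 | −1.0 (0.988) | 83.0 → 82.5 | −0.5 (0.994) |
| 60% | 81.0 → 79.0 | −2.0 (0.975) | 83.0 → 82.0 | −1.0 (0.988) |
| 70% | 81.0 → 78.0 | −3.0 (0.963) | 83.0 → 81.5 | −1.5 (0.982) |

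Worked row: 0.40 × 75 + 0.60 × 85 = 81.0; 0.60 × 75 + 0.40 × 85 = 79.0.

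**How large a shift is plausible?** If diagnosed cases double and the original half keeps its age mix, the under-five share among added cases must be 2 × w1 − w0. That is 60% for w1 = 50%, 80% for w1 = 60% and 100% for w1 = 70%. The last row is therefore the limit for a 40% starting share, because every added case would have to be under five.

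**Diagnostic yield, same shares.** With 15% at 0-4 and 5% at 5-14, the proportion moves from 9.0% to 10.0%, 11.0% or 12.0% (ratio 1.11, 1.22, 1.33). With 10% and 5%, it moves from 7.0% to 7.5%, 8.0% or 8.5% (1.07, 1.14, 1.21). The artefact can flatter the project as well as harm it.

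**Would the Z-test flag it?** Assume two-sided alpha 0.05, equal numbers per period and independent children. The probability of significance in the direction of the artefact is Φ[(|d| − 1.96 × se0) / se1], where se0 uses the pooled proportion and se1 the separate ones. For 81.0% → 79.0% with 5,000 per period:

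- se0 = √(0.80 × 0.20 × 2/5,000) = 0.0080
- se1 = √((0.81 × 0.19 + 0.79 × 0.21)/5,000) = 0.0080
- (0.020 − 0.0157)/0.0080 = 0.54, so the probability is 0.71

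| Spurious change | 500 per period | 2,000 | 5,000 |
|---|---|---|---|
| 81.0 → 80.0 | 0.06 | 0.12 | 0.24 |
| 81.0 → 79.0 | 0.12 | 0.35 | 0.71 |
| 81.0 → 78.0 | 0.22 | 0.65 | 0.96 |
| 83.0 → 82.0 | 0.06 | 0.13 | 0.26 |

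**After standardising.** Weighting the post-period bands by the baseline mix gives 0.40 × 75 + 0.60 × 85 = 81.0, a difference of 0 from baseline. This holds in every scenario because the within-band effect was set to zero.

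**The case against.** The strongest reply is that the problem is hypothetical. No section says that case finding moves toward younger children. HIV clinics, outpatient departments, wards and contact tracing are not limited to under-fives, and the baseline also extracts from MNCH, HIV and nutrition points. This stands: a reader might infer a known shift, but the documents support only a possible one. With no shift, or no age difference in the outcome, the artefact is exactly zero.

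Second, a reader might infer that the date-of-birth sentence causes the pooling. It does not. Pooling follows from Sections II.B, VII.A and IX, and deleting the sentence would not create an age analysis. It remains an obstacle, since a standardised comparison needs age in both periods. The age on the screening tool is unrestricted but cannot fill the gap: that tool is used only after the intervention starts, carries no identifiers, is collated as aggregates, and is replaced by the Pediatric TB Form in HIV clinics and contact tracing.

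Third, it is tempting to say that the economic model must assume the age mix behind deaths averted. Section VII.A describes no model structure and does not mention deaths averted. It shows only that the listed inputs are 0-14 aggregates.

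Fourth, age is only one aspect of case mix. HIV status and entry point could move the same proportions, and standardisation does not address the counts that are the project's main objectives. Both points stand. The crude effect also remains a fair description of what the programme delivered overall, so it should be kept.

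Finally, Section XIV assigns a biostatistician to develop a statistical analysis plan. Nothing beyond Section IX is available, so it cannot be checked whether age strata are added there. Any such plan would still have to deal with the restriction in Section V.A.

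**Conclusion.** The point holds in a limited form. The plan contradicts itself on the use of baseline date of birth, and it prespecifies no age-banded or age-standardised comparison although age is held in both periods. A crude before-and-after change therefore cannot be attributed to care rather than to age mix.

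The size is unknown. Under the assumed values (40% under five at baseline, up to 70% afterwards, outcome 5 or 10 points lower in under-fives, zero true effect), the spurious change in a success-type proportion is between 0 and −3 percentage points. The extreme requires every added case to be under five if cases double. A reader might infer that the Z-test will show a false harm. The table does not support that as a prediction: significance is unlikely for small shifts or small samples and likely only when both are large. The change is worth making because the data already exist, but this is not a fatal flaw.

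**What to change.** 1. **Section V.A:** reconcile the two sentences on date of birth. State that age band (0-4, 5-14), derived from date of birth or recorded age, is an analysis variable in both periods.
2. **Section IX:** report proportion indicators d, e, h, j, n and o by band and period. Beside the crude effect, give a before-and-after effect standardised to the baseline age distribution. Show the age distribution itself and the number with missing age, by period.
3. **Section VII.A:** supply the cost-effectiveness inputs by the same bands at country level, or pooled across sites where cells are sparse. Per-site monthly rates by band would often be too thin, as Table 3 expects only at least five children with presumptive TB per clinic.

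**Cost.** No new data collection is planned for this, but some baseline registers may lack age, and Section V.A already accepts that some baseline data will be unavailable. Widening the stated use of date of birth under a consent waiver, and sharing age-banded aggregates externally, is a protocol amendment that may need review by the US board and the ten country committees (Section XI.A). Cells become smaller. Case mix by HIV status and entry point remains unadjusted and should be stated as a limitation.
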